# 7.1.2.4 Pregnancies

Testing for pregnancy for a female study subject with childbearing potential must be conducted at screening (or within 7 days of dosing). Subjects who are pregnant or intend to become pregnant during the study should be excluded. Should a pregnancy occur with a study subject, the pregnancy should be reported to MediBeacon within 24 hours of the site's knowledge on the appropriate form in the Study Procedure Manual. All pregnancies will be followed to term, delivery or premature termination. Additional follow-up will occur for 3 months post-partum.

Pregnancies should be reported via email to: [contact]

## 7.1.2.5 Device Observations / Malfunctions

All device observations, malfunctions or failures of the ORFM device will be documented in the eCRF.

## 7.1.2.6 Clinical Laboratory Evaluation

All clinical laboratory assessments will be performed by a central lab. Reference ranges will be provided to the site and used by the investigator to assess the laboratory data for clinical significance and pathological changes relative to baseline measurements. The following laboratory tests will be performed as indicated in **Table 8** at timepoints outlined in **Table 4**, **Table 5**, **Table 6** and **Table 7**.

**Table 8 Summary of Clinical Safety Laboratory Assessments** 

All lab tests are non-fasting.

Chemistry Panel	Hematology	Other required lab tests

 
Alkaline Phosphatase
 
Alanine Aminotransferase (ALT)
 
Albumin
 
Aspartate Aminotransferase (AST)
 
Bilirubin (total and direct)
 
Blood Urea Nitrogen (BUN)
 
Calcium (Ca)
 
Carbon dioxide (CO2)
 
Chloride (C)
 
Creatinine (SCr)
 
Glucose
 
Phosphorus
 
Potassium
 
Sodium
 
Total Protein
 
Uric acid
 
BUN/Creatinine ratio
 
Lipids
 
Cholesterol
 
Triglycerides
 
	
 
Hematocrit
 
Hemoglobin
 
WBC
 
RBC
 
Platelets
 
Differentials
 
Neutrophils
 
Lymphocytes
 
Monocytes
 
Eosinophils
 
Basophils
 
	For WOCBP  Serum pregnancy test (screening and a urine dipstick on day of doing; and serum at the follow-up visit  Urinalysis Protein Glucose Acetone Hemoglobin (blood) Bilirubin Urobilinogen Acetone Nitrite Leucocytes pH Specific gravity Color Bacteria (when indicated) If abnormalities are seen, then microscopic examination will be performed

Chemistry Panel	Hematology	Other required lab tests
		Coagulation Parameters
		Only performed at screening and on
		dosing day
		• PT
		• INR
		• aPTT

# **7.1.2.7 Vital Signs**

Vital signs (including blood pressure, heart rate, respiration, and temperature) will be measured at screening, at multiple timepoints on dosing day (see Section 13), and at the follow-up visit. Vital signs should be collected while the subject is in a seated position and after resting for approximately 5 minutes for all measurements. Temperature is only collected at screening, predose, and the completion of the dosing day, and at the follow-up visit. In the extended PK group (Group 2) and Cohort 8 (Group 3), temperature is also taken at 1445 minutes (after the 24 hour PK collections).

# 7.1.2.8 Physical Examinations or Limited Physical Assessments

Physical examinations (when conducted by a physician) or limited physical assessments (when conducted by a nurse or other qualified personnel) should include at a minimum an assessment of the head, ears, eyes, nose, throat (HEENT), respiratory, cardiovascular, and gastrointestinal systems. It is preferred that the same medical professional perform the baseline and post dosing assessments. Significant findings that were present prior to dosing must be included in the Medical History eCRF page. Significant new findings that begin or worsen after dosing must be recorded on the AE page of the eCRF. Clinically significant abnormalities occurring post-dose should be evaluated by a physician and noted as AEs.

The study physician will assess the subject for the occurrence of clinically significant new findings that begin or worsen after dosing which must be recorded as an AE on the eCRF page. A full physical exam should be conducted at screening and limited physical assessments may be conducted at other time points and must also be inclusive of the relevant organ or body system of interest for assessing the AE

## 7.1.2.9 ECGs

Standard 12 lead ECGs will be collected at screening and various timepoints on dosing day (see (Table 4, Table 5, Table 6 and Table 7) and during the 48 hour period for Extended PK group (Group 2) and Cohort 8 (Group 3). The following parameters will be assessed: interpretation, ventricular rate, PR interval, QRS duration, QT, and QTcF.

Subjects should be allowed to rest quietly approximately 10-15 minutes prior to their ECG. Post-dose ECGs are timed to allow for this. Additional ECGs may be collected if an issue or safety concern is noted.

An appropriately trained and experienced physician will interpret the ECGs. A subject with an

abnormal clinically significant ECG at baseline or prior to dosing does not qualify for the study. A subject with an abnormal not clinically significant ECG does not qualify without investigator comment on the ECG source document/eCRF.

For changes that are clinically significant, the investigator is to continue to monitor the subject until the change returns to normal, or until the investigator determines that follow-up is no longer medically necessary, or the subject is referred to his/her primary care physician. If the investigator determines the change is not clinically significant, the investigator's evaluation will be documented on the ECG source document and no further action is required. ECGs with clinically significant abnormalities will also be reviewed by a cardiologist.

# 7.1.2.10 PK Sample Collection

PK samples will be collected at the timepoints noted in Section 13. Recommendations for venous access and sample processing information is available in the Study Procedure Manual.

# 7.1.2.11 Urine Collection

The total volume of urine excreted from the time starting pre-dose through 12 hours (or 48 hours for the extended PK subgroup) will be recorded for subjects enrolled into Groups 1 and 2 only. A sample will also be collected in accordance with the instructions provided in the Study Procedure Manual.

# 8 Information for the Investigator: Potential Risks of the Device

Adverse events that may be anticipated in this clinical study are outlined for the Investigational Drug, the ORFM Device and the Reference Standard (iohexol).

# 8.1 Investigational Drug

Clinical data from the Pilot 1A and 1B studies (total n = 32 subjects) included the following adverse events:

- Pilot 1A
  - Vasovagal reaction (1 subject)
  - o Dizziness (1 subject, 2 events)

These events occurred in fasting subjects shortly after dosing and resolved on that day. No other AEs, injection site reactions, clinically significant laboratory values or significant changes in vital signs were noted during this study.

- Pilot 1B
  - o Headaches (56.3% of subjects)
  - o Erythema (at the site of the adhesive) (100% of subjects)
  - o Diarrhoea (1 subject)
  - o Dizziness (occurring in 1 subject following release from the study center)

Erythema was thought to be related to the adhesive used to adhere the sensor to the skin. Headaches were deemed related to the head strap required to hold the forehead sensor in place.

MB-102 is excreted in the urine. Therefore, urine discoloration is expected but has not been considered an adverse event in prior studies.

In the ongoing Pilot 2 study, a total of 202 subjects with normal to compromised renal function have been exposed to MB-102. A total of 120 subjects received a dose of 4 µmol/kg followed by a 5 mL injection of iohexol. Seventy (70) subjects received a single dose only (no iohexol) of 4 µmol/kg of MB-102) and 12 have received a fixed dose of 130 mg (7 mL). All reported AEs were mild or moderate in severity and resolved without sequalae. Overall, MB-102 given in conjunction with or without iohexol was well tolerated in this subject population.

A total of 33 adverse events were reported in 22 treated subjects in Groups 1, 2 and 3 (Cohorts 5, 6 SOG and SeVG only) for an AE rate of 10.9% in the treated population. A total of 24 events in 19 subjects were considered mild and 9 moderate events occurred in 5 subjects (2.5% of the population). There were no severe events reported. There were no Serious Adverse Events (SAEs) reported during the study. There were no Unanticipated Adverse Device Effects (UADEs) reported during the study.

Four AEs, dyspepsia, chromaturia, hot flush and (facial) rash were considered related to investigational product (MB-102); all events resolved by study completion. Dyspepsia and chromaturia were also considered to be related to iohexol. Of note, chromaturia is an expected effect of MB-102 and expected in all subjects as the excretion of MB-102 will color the urine of subjects receiving the product. It is not a documented effect of iohexol (per the label).

Seven (7) AEs occurring in 7 subjects were considered related to the device (sensor attachment); these included application site erythema, dermatitis, and pruritus and were considered related to the adhesive material used to hold the sensor in place. Two events of application site discoloration (melanin spot at the sensor location) were noted in 2 subjects in the SOG cohort which resolved within 24 hours of removal of the sensor. Other reported AEs (conjunctivitis, nausea, vomiting, cardiac murmur, headache, anxiety, micturition urgency, pollakiuria, urine odor abnormal, peripheral oedema, fatigue, and a pruritis event [not at the sensor location] were considered not related to MB-102, the sensor device or iohexol. Injection site reactions (bruising, erythema, extravasation) were also not considered related to MB-102.

There may also be other risks that are unforeseen at this time. For additional information on the risk profile, please reference the current Investigator's Brochure.

## 8.2 ORFM Device

There are no direct risks associated with the ORFM device (console) as it does not contact the study subject. Adverse events observed from the sensors are with regard to the methods used to affix it to the study subject including head straps and adhesive tape (see Section 8.1).

# 8.2.1 Adhesive Clip

As with the adhesive used on the sensors, there is the chance of reaction to the adhesive used to attach the clip to the skin. Reactions could include redness, itchiness or other localized skin reactions.

#### 8.2.2 2-Part Brilliance Sensor

The 2-Part Brilliance Sensor includes a removable adhesive ring that will allow re-use of the sensor itself. There are no direct risks associated with the 2-Part Brilliance Sensor. As with the other devices described above, skin reactions may be seen to the adhesive used to hold the sensor in place.

#### 8.3 Reference Standard

Risks associated with the reference standard iohexol (Omnipaque™ 300 are detailed in the current version of the Package Insert (Appendix B).

It should be noted that the dose level of iohexol (5 mL) is significantly lower than the doses used for contrast imaging. A published study by Nilsson-Ehle in over 8000 patients using iohexol to measure kidney function reported "an extremely low toxicity" related to the small doses of iohexol administered. He reported very few adverse events compared to typical radiographic imaging studies (e.g. CT study, urography, angiography) where much larger volumes of iohexol may be used (i.e. 10-50 times). The author reported "no complications in 8000 investigations except for 2 patients who reported malaise and vomiting between 1 to 3 hours after injection of iohexol" and they concluded that they did not know if these adverse effects were related to their procedure.

## **8.4** Trial Procedures

The study will collect approximately 135 mL of blood on dosing day (PK draws and lab draws) for a standard subject in Group 1 and 2, and Group 3 Cohorts 6, SOG and Cohort 7 (Single Dose Subjects) and slightly less volume for Group 3 Cohort 5 subjects. Subjects in the extended PK subgroup (Group 2) will have approximately 165 mL of blood collected over a 48-hour period. Multiple dose subjects from Cohort 7 will have approximately 146 - 154 mL of blood collected (PK collection is reduced in this group). Blood collection may lead to light-headedness and dizziness in some study subjects. It is recommended to ensure subjects continue to hydrate and eat during dosing day to mitigate the effect of blood loss.

Bruising and pain at the site of the venous catheters may also be expected.

#### 9 Statistical Methods

# 9.1 Statistical and Analytical Plans

# 9.1.1 Datasets or Populations Analyzed

**Safety Analysis Set:** The Safety Analysis Set (SAF) will consist of all subjects who sign the Informed Consent and receive study drug in the study. All safety analyses will be performed on the safety analysis set.

**Per Protocol Set:** The Per Protocol Set (PP) will consist of all subjects who receive the investigational drug and have no major protocol deviations. Demographic and Other Baseline Characteristics including Subject's age, race, sex, weight, body mass index (BMI), baseline CKD status, and medical history will be recorded at screening and summarized for the Safety and Per Protocol Sets.

## 9.1.2 Subject Disposition

The number and percentage of subjects who complete the study or who terminate early from the study and the reasons for early termination will be collected and reported. Subjects will be considered to have completed the study if they complete the dosing day.

The number and percentage of subjects in each analysis population will be presented. Percentages will be based on the number of subjects enrolled.

#### 9.1.3 Pharmacokinetic Assessments

Pharmacokinetic parameters for MB-102 and iohexol will be calculated using both compartmental and non-compartmental techniques. Data from the patients in Cohort 1 that were used for dose ranging for MB-102 will have their data dose normalized to be consistent with the dose used for the remainder of the study. All pharmacokinetic assessments will be performed using Phoenix WinNonlin (and possibly Phoenix NLME) Build 6.4.0.768.

Non-compartmental analysis (NCA) will be performed on data for both MB-102 and iohexol. The following parameters will be determined:

- Cmax the maximum plasma concentration obtained during the sampling interval
- $T_{max}$  the time at which  $C_{max}$  occurred
- $\lambda_z$  the terminal rate constant will be determined by linear regression of the terminal linear phase of the log plasma concentration-time profile.
- AUClast Area under the plasma concentration-time curve from the time zero to the time of the last quantifiable concentration.
- AUC $_{\infty}$  Area under the plasma concentration-time curve from time zero to infinity. (AUC $_{\infty}$ ) will be calculated as: AUC $_{\infty}$  = AUC $_{last}$  + LQC/ $\lambda_z$  where LQC is the predicted concentration (based on the terminal regression) at the time of the last measurable

concentration.

- $t_{1/2} \lambda_z$  the elimination half-life will be calculated as  $t_{1/2} \lambda_z = \ln(2)/\lambda_z$ .
- Clp Total plasma clearance will be calculated as: Clp = Dose/  $AUC_{\infty}$ .
- CLr Renal clearance will be calculated as: CLr = Ae/ AUClast, where Ae is the cumulative amount of analyte excreted in urine over the sampling interval.

In addition to the NCA analysis described above, a compartmental analysis will be performed separately for each subject's profile. Based on prior data, it is expected that a two compartmental model will provide an adequate fit. In addition, a population fit may also be attempted.

Observed plasma and urine concentrations will be summarized descriptively by time point and agent (MB-102 or iohexol) for all subjects included in the pharmacokinetic analysis. In addition, plots of mean concentrations over time will be provided by agent, including standard error bars around the mean values.

All derived results for pharmacokinetic parameters will be summarized numerically by agent. For categorical variables, the frequency of subjects will be provided along with the percentage based on the number of subjects with available data. Summaries will be based on observed data (i.e., no missing data will be imputed) and will include all dosed subjects completing all aspects of the study.

An analysis of variance of estimated GFR will be performed taking into account the factors subjects, treatments (MB-102 and iohexol), CKD stage and skin color type.

[figure not shown]
All plasma and urine concentrations will be provided in listings by subject and time point. Any blood measurements obtained outside of the defined windows around the scheduled time point will be identified as protocol deviations. Additionally, pharmacokinetic parameters will be provided in listings sorted by subject.

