#### **Sensor Verification Group (SeVG)**

A Sensor Verification Group (SeVG) will consist of up to 50 subjects to validate the Brilliance sensor. Sites will enroll subjects with normal renal function to Stage 5 CKD. Subjects with normal to stage 2 CKD will be considered the "SeVG-1" group and subject to specific eligibility. Subjects who have impaired renal function (CKD Stage 3-5) will be considered the "SeVG-2" group and subject to specific eligibility requirements.

A subset of subjects (up to 20) who weigh greater than 110 lbs (50 kg) will receive a fixed dose of 7 mL (130 mg).

A study interim analysis will be performed after completion of the SeVG cohort of all previously collected subject data (Groups 1, 2 and 3 through the SevG enrollment). This analysis will be performed to summarize clinical data in support of pivotal trial regulatory discussions. It is not the intention to stop the study early or revamp sample size for the remaining cohorts.

#### Cohorts 7 and 8

An additional 48 subjects may be enrolled to test the optimized algorithm and final device design:

**Cohort 7**: up to 24 subjects with normal to CKD stage 2 renal function. A subset of Cohort 7 subjects will have 2 doses of MB-102 and will be followed for 24 hours. Single dosed cohort 7 subjects will be followed for 12 hours.

Sites enrolling subjects into Cohort 7 (multiple dose group only for Protocol Version 11.0, 12.0 and 13.0) should strive to recruit subjects with a baseline  $eGFR \geq 90$  ml/min/1.73 $m^2$  if feasible. The intent to enroll more normal subjects is to ensure clearance of MB-102 prior to the second dose in order to establish redose timelines for future subjects. In addition, subjects enrolled into the subsets of cohort 7 and 8 (Protocol Version 12.0) should strive to enroll subjects at the extremes of the Fitzpatrick Skin Scale (I and II and V and VI). Finally, subjects enrolled into Cohort 7A and 7B will an eGFR between 90 and 120 ml/min/1.73 $m^2$ . In addition, subjects in Cohort 7B will have a 24 hour period between doses (for a total post dose follow-up period of 36 + hours).

**Cohort 8**: up to 24 subjects with impaired renal function [CKD stage 3-5] will be followed for 48 hours.

Cohorts 7 and 8 will each enroll a set of subjects first to test the algorithm and

	then may be repeated if additional testing is determined to be required.

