	A subset of subjects in Cohort 7 and 8 (Cohorts 7A, 8A and 8B) will have a second sensor type placed on the pectoralis or sternum. This sensor (the 2-Part Brilliance Sensor) is being tested to evaluate a removable adhesive ring that would allow future re-use of the sensor portion.
Treatment:	Eligible subjects will receive a single dose of MB-102 followed by a single dose of iohexol (Groups 1 and 2). Group 3, Cohorts 5, 6, SOG, SeVG-1, SeVG-2 and Cohort 8 will only receive a single dose of MB-102 and will not receive iohexol. A subset of subjects in Group 3, Cohort 7 will receive 2 doses of MB-102. Blood draws will be taken at pre-defined timepoints and the Optical Renal Function Monitor (ORFM) fluorescent measurements will be collected over an 8 - 12 hour period or up to 24-48 hours in certain cohorts.
	Group 1, Cohort 1 subjects may receive a range of doses of MB-102. Assessments of coefficient of variation will determine dose optimization. Remaining Group 1 subjects and Group 2 subjects will receive the optimized dose.
	Group 3 subjects (cohorts 5, 6, SOG and over half the subjects in the SeVG cohort will receive a single dose of 4 µmol/kg. A subset of the SeVG cohort (approximately 20 subjects who weigh greater than 110 lbs (50 kg) will receive a fixed dose of 7 mL (130 mg) MB-102.
	Cohorts 7 and 8 (regardless of weight) will all receive a fixed dose of 130 mg (7 mL).
	A subset of Group 3 subjects in Cohort 7 will receive 2 doses of MB-102 (fixed dose of 7 mL (130 mg). The 2 nd dose will be administered 12 hours after the first dose. For Cohort 7B, subjects will receive their 2 nd dose 24 hours after the first dose.
	Sensor placement in all subjects from Groups 1 and 2 will be in two different locations. All Group 1 and 2 subjects will have a single sensor placed on the sternum. A second location will be assigned to determine additional sites for fluorescent measurements. Group 3 subjects may have 2-3 different sensors located on different parts of the body. At least one sensor will be on the sternum or pectoralis major.  • Group 1 subjects will have fluorescent measurements performed by the
	
 
Prototype QuantumLeap device.
 
Group 2 subjects will have fluorescent measurements performed by the Prototype Radiance device.
 

	Group 3 subjects will have fluorescent measurements performed by the Prototype Brilliance device.

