#### 5.2.2 Group 3 Dosing

Subjects enrolled in Group 3, Cohorts 5, 6, SOG and part of the SeVG group will receive a dose of 4 µmol/kg of MB-102. No dose optimization work will be conducted.

A subset of SeVG subjects (up to 20 subjects who weigh greater than 110 lbs [50 kg]) and all subjects in cohorts 7 and 8 will receive a fixed dose of 7 mL (130 mg). This dose is equivalent to what a 191 lb subject would receive if dosed at the standard 4 µmol/kg dose level. This dose change is within the safety margin of previously performed non-clinical studies. The purpose of testing a fixed dose level is to determine if such a dose will be adequate across a variety of subject weights and still remain an accurate measurement of tGFR. A fixed dose level would simplify dose preparation when the product goes to market.

A subset of subjects enrolled into Cohort 7 will receive 2 doses of MB-102 (both doses will at the fixed dose level of 7 mL or 130 mg). The 2nd dose of MB-102 will be administered either 12 hours or 24 hours (Cohort 7B) after the first dose.

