# Group 1 Cohort 1 (30 subjects), Group 2 Cohort 3 (20 subjects) and Group 3: Cohorts 5 (8 subjects), SOG Cohort (up to 27 subjects), SeVG-1 (up to 25 subjects) and Cohort 7 (up to 16 subjects)

- Are healthy as determined by medical history, with no clinically significant findings on screening and baseline physical exams, vital signs and clinical laboratory panels or conditions that could adversely impact the subject's participation or safety, conduct of the study or interfere with study assessments
- Have eGFR (CKD-EPI equation) of ≥60 ml/min/1.73m² (normal to Stage 2 CKD) at the time of screening

Approximately half of the patients enrolled in each cohort will have Fitzpatrick Scale Type I, II or III skin color type and the other half will have Fitzpatrick scale Type IV, V or VI skin color type.

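### Section 9.1.3 normalises dose for Cohort 1 only, so the MB-102 concentration, Cmax and AUC summaries pooled by agent mix 4 µmol/kg with a fixed 130 mg dose (minor; clearance and GFR results unaffected)

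*Combined protocol and SAP*

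**What the plan says.** Section 9.1.3 states that the Cohort 1 subjects used for MB-102 dose ranging "will have their data dose normalized to be consistent with the dose used for the remainder of the study". It gives no other normalisation rule. It summarises plasma and urine concentrations for each agent at each time point and plots mean concentrations by agent with standard error bars. For parameters, "All derived results for pharmacokinetic parameters will be summarized numerically by agent". The same paragraph says the summaries cover every dosed subject who completes the study. No split by dose, cohort or group is given for these outputs, and Section 9.1.1 defines no PK analysis set.

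On dosing:
- Sections 5.2.1 and 5.2.2 give 4 µmol/kg to Group 2, Cohorts 5 and 6, the SOG and part of the SeVG.
- For the rest of the SeVG, the synopsis says: "A subset of subjects (up to 20) who weigh greater than 110 lbs (50 kg) will receive a fixed dose".
- Section 5.2.2 adds that "all subjects in cohorts 7 and 8 will receive a fixed dose of 7 mL (130 mg"). The synopsis repeats this with no weight limit: "Cohorts 7 and 8 (regardless of weight) will all receive a fixed dose of 130 mg (7 mL").
- Section 8.1 reports, for the subjects who also had iohexol, "A total of 120 subjects received a dose of 4" µmol/kg. Only Groups 1 and 2 had iohexol.

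**The concern.** The rule presupposes one reference dose for everyone outside Cohort 1. That no longer describes the study. The subjects the rule names seem all to have received the standard dose, and the subjects on a different dose per kg have no rule.

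Concentrations, Cmax and AUC scale with dose. Pooled by agent, they describe neither dosing scheme. This matters because Section 5.2.2 says the fixed dose is being tested for adequacy across body weights, and Section 4 lists the optimum dose as an objective. A pooled table cannot show how exposure differs between the schemes.

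Cohort 7 adds a further gap. Samples after the second dose reuse the nominal times of the first (5, 120, 180 minutes and so on), and nothing in Section 9.1.3 keeps the two profiles apart.

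**Working it through.** **1. Molar conversion, checked against the plan's own figure.** Section 3.2, Table 1 equates 200 µmol/kg with 74.4 mg/kg, so 1 µmol is 74.4/200 = 0.372 mg and 4 µmol/kg is 1.488 mg/kg. The weight at which 130 mg equals 4 µmol/kg is 130/1.488 = 87.4 kg, or 192.6 lb. Section 5.2.2 states 191 lb, so the figure is reproduced to within 1%.

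**2. Dose per kg under the fixed dose.** 130/0.372 = 349.5 µmol. Divide by weight W for dose per kg; multiply fixed-dose data by 4W/349.5 to scale to 4 µmol/kg.

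| Weight | µmol/kg | Ratio to 4 µmol/kg | Scaling factor |
|---|---|---|---|
| 50 kg | 6.99 | 1.75 | 0.57 |
| 70 kg | 4.99 | 1.25 | 0.80 |
| 100 kg | 3.49 | 0.87 | 1.14 |
| 120 kg | 2.91 | 0.73 | 1.37 |

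Only 50 kg is in the documents, as the limit for the SeVG subset. The other weights are assumptions. If PK is dose-proportional (assumed), concentrations, Cmax and AUC shift by the same ratios at equal clearance and volume per kg.

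**3. How many subjects.** For Cohorts 7 and 8 the synopsis says: "An additional 48 subjects may be enrolled to test the optimized algorithm and final device design". Table 2 gives 24 + 16 + 8 = 48. With the SeVG subset, 20 + 48 = 68 subjects: 68/141 = 48% of Group 3 and 68/261 = 26% of the study. The totals agree: 8 + 8 + 27 + 50 + 48 = 141, and 60 + 60 + 141 = 261. The Section 5.5.2 headings differ: one lists "and Cohort 7 (up to 16 subjects"), the other 16 for Cohort 8. That gives 20 + 16 + 16 = 52, but Group 3 would then sum to 125 rather than 141. Section 8.1 reports 12 fixed-dose subjects treated at that point.

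**4. Effect on a whole-study mean.** With a share of 68/261 = 0.261 and every fixed-dose subject at one assumed weight, the shift is 0.261 × (ratio − 1):
- 60 kg (ratio 1.456): about +12%
- 70 kg (1.248): about +6%
- 80 kg (1.092): about +2%
- 100 kg (0.874): about −3%

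**5. The mix changes along the curve.** After 720 minutes, single-dose samples come only from about 10 Cohort 4 extended-PK subjects on 4 µmol/kg (Section 5.3.1) and from Cohort 8 on 130 mg (Section 5.3.2). At planned maxima:
- 960 and 1440 minutes: (16 + 8)/(16 + 8 + 10) = 24/34 = 71% on the fixed dose
- 1920 to 2880 minutes: 16/(16 + 10) = 16/26 = 62%

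This leaves out Cohort 7B's draw before its second dose.

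**6. What does not move.** Section 9.1.3 computes clearance as dose over AUC to infinity, so dose is already accounted for. The terminal rate constant, half-life and Tmax do not depend on dose size under linear PK.

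**The case against.** The strongest reply is that nothing primary depends on this. The MB-102 versus iohexol comparison uses Groups 1 and 2, where all 120 subjects are reported at 4 µmol/kg. The Group 3 endpoint compares transdermal GFR with plasma GFR, and plasma GFR rests on clearance. What remains is descriptive output in a pilot that Section 5.5.1 calls hypothesis generating, and by-subject listings would allow any split later. This stands, and it is why the point is minor.

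A second reply is that Section 9.1.3 was written for Groups 1 and 2, since it refers to urine and iohexol, which Group 3 does not have. That may be its origin, but the text does not limit the section and its population wording takes in Group 3. Nor does the protocol defer PK grouping or normalisation to a separate SAP: Section 9.1.4 defers laboratory detail and Section 9.1.8 possible imputation rules.

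A reader might infer that the standard error bars would show dose mix instead of PK variability. The documents do not support that. Over 50 to 120 kg, dose per kg varies 6.99/2.91 = 2.4-fold, and only among fixed-dose subjects. Eligibility limits alone (eGFR 15 for Cohort 2, up to 120 for Cohorts 7A and 7B) imply 120/15 = 8-fold in AUC at equal dose, taking eGFR as a stand-in for clearance, and Stage 5 CKD widens it. Renal function would dominate the bars; dose mix adds to them.

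**Conclusion.** The point holds as a minor gap in the descriptive PK reporting. As written, Section 9.1.3 pools two dosing schemes in the concentration, Cmax and AUC outputs, and its one normalisation rule appears to cover nobody who needs it. For an individual on the fixed dose the distortion runs from +75% at 50 kg to −27% at an assumed 120 kg. For a whole-study mean it is about −3% to +12% if all fixed-dose subjects share an assumed weight between 100 and 60 kg. It matters most after 720 minutes, where most single-dose samples would come from fixed-dose subjects.

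These sizes assume dose-proportional PK, the weights shown and planned maximum enrolment. The count of 68 is a ceiling.

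It would be wrong to infer that the GFR results or either primary comparison are biased: clearance, half-life, Tmax and plasma GFR do not depend on this rule.

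**What to change.** In Section 9.1.3, replace the Cohort 1 sentence with a rule for all subjects:
- Tabulate and plot MB-102 concentrations, Cmax, AUClast and AUC∞ separately for 4 µmol/kg, 130 mg first dose and 130 mg second dose, by CKD stage.
- Before any display that pools dosing schemes, normalise to actual dose per kg (for example, scaled to 4 µmol/kg) and name that unit. Dividing by total milligrams would add body-size variation to the weight-dosed data.
- Compute clearance from the actual administered dose and un-normalised AUC, so that dose is not corrected for twice.

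The cost is SAP wording and extra table columns. Weight and administered dose are already part of the study record, so no new data are needed.
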